# **13** Qualitative Sub-study

Materials for the sub-study and directions for the participants can be found in the appendices of this protocol (20a and 20b). The following sections are focused on the details of the sub-study.

# 13.1 Subsample

A nested subsample will be selected from the survey participants that are receiving antenatal care at University College London Hospital (UCLH) to take part in a set of at-home journal activities. Comprising 30 participants, the nested sample will be broken-down into three groups: 1) cisheterosexual parents (n=10), 2) LGB+ cisgender parents (n=10), and 3) transgender parents (n=10). UCLH study participants can opt-in to the sub-sample while completing the first panel survey, wring the journal activity screening.

using the journal activity screening questions provided (appendix 16). Participants from UCLH will be asked in the first panel survey if they have interest in participating in the qualitative sub study and completing journal activities. The survey responses of those

Table 5: Qualitative Sampling Approach						
	Cishetero.	Cis-LGB+	Trans*			
High Res./Low Vul.	5	5	5			
High Vul./Low Res.	5	5	5			

participants indicating interest will be examined to guide purposive sampling (i.e., non-homogeneity of vulnerability and resilience scores). Selecting a balance of the higher and lower scores follows an extreme-case approach as an means of integrating qualitative and quantitative data.

# 13.2 Recruitment

Participants who are taking part in the study at UCLH will be asked at the end of their first survey if they would be interested in participating in the qualitative sub-study.

After completing the first survey, the resilience and vulnerability psychometric scales will be scored through calculated variables on REDCap (appendix 16). These scores will give an idea of which participants meet the extreme-case criteria discussed in section 13.1 above. If a participant is interested in the sub-study, their resilience and vulnerability levels as composite scores will be reviewed and compared. What is being review is whether at least one of their composite scores is
either extremely high or low in comparison with the other score. For example, a participant with middling values for both scores would not be eligible, while a participant with extremely high resilience and extremely low vulnerability would be an ideal candidate.

# 13.3 Consent

Before participating in the qualitative sub-study, interested participants will have to complete an additional consent form (appendix 17) that will be completed prior to receiving the journal activities below, after reading the sub-study PIS (appendix 18). This will follow the same approach as the main study, with an electronic consent form that is kept separate from the participants record with a copy immediately emailed to the participant for their records.

# **13.4 Qualitative Data Collection**

At the end of the first panel survey, participants at University College London Hospital (UCLH) will be asked if they are interested in completing an at-home journal activity before being screened and assessed for their eligibility (see Table 1 on page 21). When eligible, they will be asked about their preferred methods of completing the journal activities (appendix 19). Participants can choose from two completion and submission processes as part of this form: 1) the digital packet to be uploaded or mailed-in when complete with postage paid (appendix 20a) or 2) a hard copy A5 journal (appendix 20b), to be mailed to the participant, with submission directions and/or a postage paid return envelope. Multiple options have been made available to allow for variations in participants' level of digital literacies.

# **13.5** Journal Activities

To aid participants with writing in their journals, whether hard copy (appendix 20a) or digital (appendix 20b), there are three prompts as mapping exercises included within the journal. These prompts are included along with directions for the journal activities, which clarify to participants that there is no wrong way to use the mapping prompts and no wrong way to complete the journal activity.

The prompts, in the form of maps, will serve as a tool to help participants determine what they want to include within the journals rather than as a source of data. Though they may help connect the quantitative and qualitative data chronologically. The first journal map has prompts that focus on events during pregnancy, broken down into four sections: pre-conception, first trimester, second trimester, and third trimester. The second map's prompts focus on events during labour and delivery, including right after the birth as: early labour, active labour, birth, recovery. While the third map's prompts focus on the first month postpartum, inclusive of the first infant check-up, along with the participant's own recovery and adjustment period.

This at-home journal activity is expected to take no longer than two hours to complete with no expectation for what the participants will include beyond the pregnancy and childbirth themes mentioned by the mapping prompts. This time estimate is assuming that participants my take up to an hour to write about their experiences while pregnant, and up to another hour to write about their experiences after giving birth or experiencing a loss, and any experiences postpartum they feel are relevant. This estimate of two hours is the equivalent amount of time that would be scheduled if an interview were conducted at each of these time points. However, with the journal activities, participants will be able to instead work at their own pace, write privately, and be able to complete the activity in a safe space. As the activity is not being timed and will vary between participants, it could also take as little as 30 minutes to complete the activity in its entirety. When complete, participants will confirm completion and submit their journals via a submission form (appendix 21).

# **14 QUALITATIVE AND QUANTITATIVE ANALYSIS**

# 14.1 Structural Equation Modelling

Using the free data analysis software R and the lavaan package, the quantitative data will be analysed using longitudinal Structural Equation Modelling (SEM). This combines the panel survey data and patient record data within a test of a hypothesized model (Figure 4). This statistical method will allow for the hypothesized roles of resilience and vulnerability to be tested through using the questions that are being asked in the survey instruments. When it is not possible to directly observe concept, latent (i.e., unobservable) variables can become measurable by recording observable components of those concepts. For this study, the observable variables, discussed in the survey instruments sections, define resilience and vulnerability and how these concepts link into the health of the gestational patient, and how they also link into their pregnancy and birth outcomes. These variables are laid out visually in Figure 4 on page 34. The fit of the model will be compared between LGBTQIA+ participants and cisgender heterosexual participants in order to examine inequality in health and their explanatory processes across the two subsamples.

# 14.2 Narrative Analysis

The qualitative data collected through the journal activities will be analysed using narrative analysis, following the key themes and events that the participants have chronicled during their pregnancy and within the month after birth. Narrative analysis is a grouping of methods that are used for the analysis of texts, specifically as a method of organising meaning and providing chronological structure to events and human actions from parts into a whole. Narrative analysis allows for the review of participant's experiences and navigation throughout antenatal care, childbirth, and postpartum, making the most out of the study's methods.

Providing explanations and explorations in the narratives of LGBTQIA+ pregnancy and parenthood will enable a dialectical approach to data integration within the analysis (discussed on page 32) while also being able to account for additional points of concern and minority stressors (e.g., fear of childbirth), and to allow for further discussion of resilience responses.

Once the journals are received from participants, depending on if they are hand written or typed, the information will be input into NVivo on the Data Safe Haven to be transcribed and notated, as necessary. After the initial process of establishing the themes, responses will be organised into chronological narrative arcs, with the themes noted.

# 14.3 Integration of study and sub-study data

The data from the study and sub-study are being collected in a way to allow for them to work together in the analysis process. This is being done by allowing the data to "speak to each other" as a way to better understand the bigger picture. With two survey points and a sub-study with a journal activity in-between, this allows for both the qualitative data and quantitative to have a narrative arc, which means that resilience and vulnerability elements can be mapped with medical data to deepen what is observed in the participants' experiences.

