**REC** – Research Ethics Committee

**Resilience** – A psychosocial construct defined as a phenomenon or process that is uses intrapersonal, interpersonal, sociocultural, economic, and political resources as a means of resistance or recovery from negative pressures/influences, such as stress, stigma, and discrimination. Often synonymous with protective factors.

SAR – Serious Adverse Reaction

SAE - Serious Adverse Event

**Social infertility** – Availability of only one gamete type in a partnership, requiring proof of biological infertility.

**Structural Equation Modelling (SEM)** – A quantitative method, using both observed and latent variables, used to test hypotheses within a model.

SOP - Standard Operating Procedure

**SSI** – Site Specific Information

Subdimension - A measurable, observable component of a construct.

TMF - Trial Master File

**Transgender** – An adjective used to describe someone who identifies as a gender other than the sex that they were assigned at birth.

UCLH – University College London Hospital

**Vulnerability** – A term used by bioethicists and researchers meaning a state of being and context in which power and/or interdependency effects the ability to act or react to internal and external stimuli, thereby diminishing tolerances of stress, stigma, and discrimination as it influences mental and biological processes. These processes may be relevant to both susceptibility to illness and/or the ability to recover from adverse health events. Often synonymous with risk.

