# 12.3.2 Longitudinal Panel Survey

Using existing, validated scales, identical panel surveys will assess for differences in resilience and vulnerability scores in pregnancy (survey 1) and postpartum (survey 2). The Research Electronic Data Capture (REDCap) survey platform (see appendix 13) will collect data securely, allowing survey responses to be stored directly onto a digitally secure remote server that will be accessed by the study team (i.e., the Data Safe Haven—see appendix 14). Data extracted from patient records will be linked to participants survey responses after participation via data entry forms in the secure REDCap platform.

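### The journal writers' Survey 1 to Survey 2 arc starts at the extreme score that selected them, so part of any apparent recovery or decline may be regression to the mean

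*Protocol*

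**What the plan says.** Section 13.1 draws the sub-study from UCLH survey participants who opt in, in three groups: "1) cisheterosexual parents (n=10), 2) LGB+ cisgender parents (n=10), and 3) transgender parents (n=10"). Table 5 divides each group into five writers with the "High Res./Low Vul" profile and five with the reverse. The stated principle is: "Selecting a balance of the higher and lower scores follows an extreme-case approach".

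Section 13.2 fixes when the selection score is taken: "After completing the first survey, the resilience and vulnerability psychometric scales will be scored through calculated variables on REDCap". People who score mid-range on both composites are ruled out, and "a participant with extremely high resilience and extremely low vulnerability would be an ideal candidate". No numerical cut-off is given.

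Section 12.3.2 says that "identical panel surveys will assess for differences in resilience and vulnerability scores in pregnancy (survey 1) and postpartum (survey 2"), so the same scales are repeated. Section 14.3 joins these two survey points to the journal written between them and says "this allows for both the qualitative data and quantitative to have a narrative arc", with the resilience and vulnerability elements mapped onto what participants describe.

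The glossary defines resilience partly "as a means of resistance or recovery from negative pressures/influences".

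**The concern.** Only the 30 writers have journals, so the integration in 14.3 concerns people who were chosen for extreme Survey 1 scores. A score picked for being extreme contains, on average, error or transient variation in the direction of selection. On an identical second survey that part is not expected to recur, and the group mean moves back towards the population mean without any true change.

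The two Table 5 profiles would drift in opposite directions. The high-vulnerability, low-resilience row would look as if it were recovering, and the other row as if it were losing resilience. Because recovery is part of the protocol's own definition of resilience, the artefact resembles the phenomenon being studied. Journal content could then be used to explain movement that selection produced. The protocol mentions no second baseline, no comparison with unselected participants and no conditioning on Survey 1.

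**Working it through.** **Plan's own figure.** Three groups × two profiles × five writers = 30, as stated.

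**Inputs from the protocol.**
- Selection on Survey 1 only (13.2), five writers per cell (Table 5), and identical scales at both surveys (12.3.2).
- Main sample of 600 cisgender heterosexual and 200 LGBTQIA+ participants (8.2.1), eleven sites (8.2.2), journals at UCLH only (13.1).
- Planning figures of 3% LGBTQIA+ and about 0.7% transgender (8.2.3.2).

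**Inputs that must be assumed.** The protocol gives no retest correlation *r*, UCLH share or opt-in rate. I take *r* from 0.6 to 0.9 and a UCLH share from 1/11 to 1/4. I treat selection as the five most extreme of *n* on one standardised score. That is a simplification, because 13.2 compares a person's two composites and does not describe a ranking.

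**Formula.** With no true change, the expected Survey 2 minus Survey 1 score is −(1 − *r*) × E[z | selected]. E[z | selected] is the mean of the five most extreme of *n* standard normal scores, obtained by simulation with 20,000 runs.

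| Pool *n* | Mean at Survey 1 (SD) | *r* = 0.6 | *r* = 0.7 | *r* = 0.8 | *r* = 0.9 |
|---|---|---|---|---|---|
| 12 | 0.87 | 0.35 | 0.26 | 0.17 | 0.09 |
| 27 | 1.39 | 0.56 | 0.42 | 0.28 | 0.14 |
| 40 | 1.60 | 0.64 | 0.48 | 0.32 | 0.16 |
| 55 | 1.75 | 0.70 | 0.53 | 0.35 | 0.18 |
| 150 | 2.18 | 0.87 | 0.66 | 0.44 | 0.22 |

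The last four columns give the drift in SD per row. For example, *n* = 55 and *r* = 0.6 gives 0.4 × 1.75 = 0.70. Over the whole table the drift runs from 0.09 to 0.87 SD, with opposite signs in the two profiles.

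**Selection on the contrast.** Suppose writers are instead chosen on resilience minus vulnerability (correlation between composites −0.3, *r* = 0.7, both assumed). The resilience score then moves by about 0.22 SD at *n* = 12, 0.43 at *n* = 55 and 0.53 at *n* = 150. This is smaller, but in the same direction.

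**Pools by group.**
- A 1/11 share gives 600/11 ≈ 55 cisgender heterosexual and 200/11 ≈ 18 LGBTQIA+ participants. If 0.7/3 of the latter are transgender, that is about 4 transgender and 14 cis-LGB+.
- A 1/4 share gives about 150, 38 and 12.
- With the 1/4 share, full opt-in, rank selection within group and *r* = 0.7, the drift per row is about 0.66, 0.48 (using *n* = 40) and 0.26 SD.
- With the 1/11 share, the assumed LGBTQIA+ pool of 18 is smaller than the 20 LGBTQIA+ writers that Table 5 requires, so no comparable figure can be given.
- If half of 55 comparators opt in, *n* is about 27 and their drift at *r* = 0.7 falls from 0.53 to 0.42 SD.

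**The case against.** The strongest reply is that 14.3 specifies no analysis of change. It names no change score, row average or contrast between groups among the 30 writers. The questions that the journals serve (4.2.1 to 4.2.3) are about narratives, and how scores are laid beside text could be left to an analysis plan. This stands in part: the risk lies in interpretation, and no planned test is invalid. It does not remove the point, because the protocol itself fixes both the selection score and its reuse as the start of the arc.

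It is also right that the remark on score differences in 12.3.2 describes the panel of all 800, who are not selected on Survey 1. The longitudinal structural equation model in 14.1 is therefore untouched, as is the narrative analysis of journal text in 14.2. Extreme-case sampling is a legitimate choice for the qualitative aim. True postpartum change may add to the drift or mask it.

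A reader might go further and infer that the artefact would make cisgender heterosexual parents seem to recover more than LGBTQIA+ parents, since equal quotas are filled from unequal pools. The documents do not support that:
- Each group has five writers in each of two opposite rows. In the symmetric model above, the drifts cancel within a group, so such a difference appears only if one row is read alone.
- Whether the drift differs, in which direction and by how much, depends on opt-in and on whether selection is by rank within group or by a common cut-off. Section 13.2 does not say.
- Five-person cells are too small to show a modest difference. At *r* = 0.7, the standard error of the difference between two cell means at Survey 2, given Survey 1, is √(1 − 0.49) × √(2/5) ≈ 0.45 SD.

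**Conclusion.** The point holds as a caution about the mixed-methods integration. The first point of each writer's arc is the score that selected them, so some Survey 1 to Survey 2 movement is expected from selection alone whenever the retest correlation is below 1. The direction within each row follows from the design, but the size does not. The figure of about 0.1 to 0.9 SD per row rests on the assumed pools of 12 to 150, the assumed retest correlation of 0.6 to 0.9, and selection of the five most extreme per tail. A group difference in drift is possible but not established. No primary question depends on this, and the change is a worthwhile, inexpensive improvement.

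**What to change.** In 14.3, state that a writer's raw change from Survey 1 to Survey 2 will not be read as recovery or decline. Show each writer's Survey 2 score beside the Survey 2 score expected for main-study participants with the same Survey 1 score, taken from a regression in all participants who completed both surveys. If that relation is modelled adequately, the expected drift from selection is removed.

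Report the full-sample mean change in each group beside this benchmark. Residuals from a regression average zero in the set to which it is fitted, so without that figure a true average change from pregnancy to postpartum, or a true group difference in it, would vanish from the integration.

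In 13.1, add a sentence that some convergence of the two Table 5 rows is expected from selection alone.

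The cost is a short paragraph, one regression per composite on data already being collected, and a presentation harder to explain than raw change. If the benchmark is fitted within LGBTQIA+ participants, it also pools cis-LGB+ and transgender participants, whom 13.1 keeps apart.

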# **15 FUNDING AND SUPPLY OF EQUIPMENT**

The study funding has been reviewed by the UCL Research Office and deemed sufficient to cover the required the study activities, as the PhD student will be responsible for the majority of the study tasks. NHS costs have been projected as zero per site because of the PhD student providing the efforts necessary for the project, with site support available through the Local Clinical Research Network when the site already has support in-place. There are no care costs or changes in procedure to incur further cost associated with this study. This has been discussed with each study site during the planning process. The project is being sponsored through a doctoral studentship that is overseen by the UBEL Doctoral Training Partnership with funding provided by the ESRC (Grant Reference: ES/P000592/1).

The funds that are covered through the Doctoral Training Partnership include tuition for the PhD Student and annual maintenance, with a London allowance. At present, there is no further funding available or necessary for the study to take place.

# **15.1 Conflict of Interest Statement**

There are no conflicts of interest for the CI of the project or any other investigator/collaborator. This means that there is not any direct personal involvement (e.g. financial, shareholding, personal relationship, etc.) in the organisations sponsoring or funding the research that may give rise to a potential conflict of interest.

# **16 DATA HANDLING AND MANAGEMENT**

The study complies with the requirements of General Data Protection Regulation (2016/679) and the Data Protection Act (2018). All investigators and study site staff will comply with the General Data Protection Regulation (2016/679) regarding the collection, storage, processing and disclosure of personal information, and will uphold the Act's core principles. UCL is the data controller; the UCL Data Protection Officer can be reached through [contact]. As this is a student project, the data processors for the data from all four sites are [name] (PhD Student), [name] (CI/PhD Supervisor), and [name] (Co-Supervisor). Figure 1 explains the flow of information from each site to the study team, who will use the Data Safe Haven to complete all the steps for the project to be completed securely.

The study will collect the personal data laid out in the attached survey measures as they are necessary for the assembly of the vulnerability and resilience constructs. Examples of the personal data to be collected directly from the participant through the study measures are:

- Name
- Hospital ID no.
- Date of Birth (used for age and linkage)
- Email address (used for recruitment and linkage)
- Gender
- Sexual Orientation
- Partnership status
- Education Level
- Employment Status
- Boroughs for living and working (depreciation score)
- Mode of transportation
- Ethnicity

Patient data that will be extracted from the electronic health records includes:

- Gestational patient: Blood Pressure
- Gestational patient: Urinalysis
- Gestational patient: Height
- Gestational patient: Weight
- Gestational patient: BMI
- Gestational patient: Routine blood draw (i.e., white blood count, etc.)
- Gestational patient: Fundal Height
- Gestational patient: Additional measures as relevant (as covariates/control variables)
  - Pre-existing conditions (i.e., PCOS, diabetes, etc.)
  - Any further antenatal tests (as requested by care team)
  - Details on birth (i.e., length of labour, interventions, etc.)
  - Complications for parent (i.e., maternal mortality, length of hospital stay, etc.)
  - Any further tests requested by care team related to pregnancy/labour/recovery
- Infant: APGAR Score
- Infant: Gestation length
- Infant: Birth Weight
- Infant: Height/length
- Infant: Head circumference
- Infant: Additional measures as relevant (as covariates/control variables)
  - Complications (i.e., further monitoring, need for time in NICU, miscarriage/stillbirth/infant mortality, etc.)
  - $\circ$  Care processes (i.e., skin-to-skin time, supplementation, etc.)
  - $\circ$  Any further tests requested by the care team related to infant health

Data transfer between the hospital sites and the data processors will take place over the secure network provided by the Data Safe Haven, hosted by UCL. The Data Safe Haven is a remote server that uses a wall-garden approach to allow for the securing of identifiable data in a way that meets NHS standards. This is done through a two-factor security approach that relies on both a password and a fluctuating key fob that cycles through the secondary authentication code. The core research team (PhD student, CI/Primary supervisor, and Co-supervisor) will be the only members with direct access to the data, which is a limit placed to ensure patient-participant confidentially across a multisite project. The Data Safe Haven also provides a secure storage method - both within the timeline of the study and in compliance with the necessary archival of the data associated with the project. Data collection through REDCap on the Data Safe Haven keeps the assurances laid out in appendix 15, as it cordons off the survey responses directly to the 1 terabyte server space set aside for the Data Safe Haven project that is registered with IT at SLMS at UCL.

All personal, identifiable data will be kept separate from the data that will be analysed in order to protect the safety and security of their identity and information. Records will be linked using a randomly generated participant identification number. Only the PhD student will have access to the dataset that has the identifiable data in order to ensure responses are linked correctly. This will allow for a de-identified dataset during the analysis process. Upon completion of the study the anonymised data will be archived on the Data Safe Haven. Personal data, without permission to contact for future research, will be stored or accessed less than 3 months after the study has ended.

Figure 4 - Flow of data from sites to Data Safe Haven

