# 4.3 Primary Scientific Aim

An assessment of vulnerability and resilience resources on birth outcomes and neonatal health using Structural Equation Modelling and a journal activity.

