# **16.2** Sensitive Data and Confidential Advisory Group Review

Because of the methods needed to recruit patients, there is advice being using the contact information that is available in their health records, this project is seeking permission to access this information prior to receiving consent. There will also be confidential and sensitive information that is being requested about biomedical tests that are standard within antenatal care which comprise the variables in the analysis. Aside from contact information and antenatal test results, the rest of the patient information being requested deals with data variables and the ability to link responses to patient records with accuracy.

The identifiers that we will request access to will be for either the purposes of linking patient records and survey responses, or for model building and data analysis. For the linkage of patient records and survey responses, we will need:

- Name (Patient Records)
  - To ensure that the right patient record has been located properly for linking
- Hospital ID no. (Patient Records)
  - For locating and linking infant health records
- Date of Birth (Survey)
  - Used to calculate age, risk, assessing eligibility for study, linking to patient records
- Date of Death (Patient Records)
  - To assess for maternal mortality within the samples
- Geographic identifiers (Survey)
  - The post code for the live and work boroughs collected will be used for assigning the deprivation index value as a structural indicator of vulnerability.

In order to develop the SEM for data analysis, the following identifiers are necessary:

- Date of Birth (parent, Survey)
  - Used for calculating age
- Date of Birth (infant, Patient Records)
  - Used for calculating gestational length
- Date of Death (parent and infant; Patient Records)
  - To assess for infant and parent/maternal mortality within the samples
- Gender (Survey)
  - This is special category data that is necessary because of irregularity in collecting gender as a non-binary variable in-clinic and being a key variable in the research objectives
- Sexual Orientation (Survey)
  - Another variable that is necessary to fulfil the key research objectives
- Ethnicity (Patient Records)
  - Necessary to fulfil the key research objectives to assess for minority stress

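### Section 16 labels birth complications, NICU time, pregnancy loss and deaths as control variables, while other sections treat them as outcomes; followed as written, this would bias the birth and neonatal paths.

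*Protocol*

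**What the plan says.** Section 16 lists the record data in two kinds. Apgar score, gestation length, birth weight, length and head circumference are listed for the infant with no role attached. Two further blocks carry a role: "Gestational patient: Additional measures as relevant (as covariates/control variables" and "Infant: Additional measures as relevant (as covariates/control variables".

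The parent block begins with "Pre-existing conditions (i.e., PCOS, diabetes, etc" and goes on to "Details on birth (i.e., length of labour, interventions, etc" and "Complications for parent (i.e., maternal mortality, length of hospital stay, etc". The infant block contains "Complications (i.e., further monitoring, need for time in NICU, miscarriage/stillbirth/infant mortality, etc", followed by care processes. Both blocks also have an open entry for further tests.

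The primary aim in section 4.3 is "An assessment of vulnerability and resilience resources on birth outcomes and neonatal health", by structural equation modelling (SEM) and the journal activity. Section 16.2 asks for parent and infant dates of death among the identifiers needed to develop the SEM, with the purpose "To assess for infant and parent/maternal mortality within the samples".

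**The concern.** A control variable on the path from an exposure to an outcome should precede the exposure, or at least not result from it. Pre-existing conditions meet that test. NICU time, stillbirth, neonatal death, maternal death, birth complications and length of stay do not, when the exposure is vulnerability or resilience measured in pregnancy. They occur after survey 1, and they are birth or neonatal outcomes or follow from them.

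Adjusting for a consequence of the outcome pulls the exposure coefficient towards zero. Adjusting for a post-exposure event that shares unmeasured causes with the outcome can open a collider path and distort the coefficient. In plain terms, a stillbirth or a NICU admission would be adjusted away when it should count as a poor result. The paths at stake are those that answer the neonatal question in section 4.1.2 and the primary aim in section 4.3.

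**Working it through.** The protocol gives no figure on this point, so there is none to reproduce. The check has two parts.

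**1. The sections side by side**

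| Item | Role in section 16 | Role elsewhere |
|---|---|---|
| Complications of pregnancy or birth | Control variable (parent and infant blocks) | Section 12.3.1.1, on pregnancy outcomes and neonatal health, places them with the outcome measures |
| Infant and maternal death | Control variable | Section 16.2: to be assessed, under the data needed for the SEM |
| NICU time, pregnancy loss, parental length of stay | Control variable | Fall under the birth outcomes and neonatal or parent health of sections 4.3 and 14.1 |
| Length of labour, interventions, infant care processes | Control variable | No other role stated; they occur after survey 1 |
| Pre-existing conditions | Control variable | No conflict |
| Apgar, gestation length, weight, length, head circumference | No role label | Section 12.3.1.1: outcome measures; no conflict |

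Section 14.1 links resilience and vulnerability to parent health and to pregnancy and birth outcomes. It names no control variables and does not withdraw the section 16 label.

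**2. Direction and possible size of the bias**

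Every parameter here is assumed. One million records were simulated per scenario.

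- V (vulnerability) and U (an unmeasured cause) are independent standard normal variables.
- Neonatal health: Y = -0.3V - uU + e, with the variance of e set to 1 - 0.09 - u², so that Y has variance 1. The true total effect of V is -0.30.
- The complication C is the top 10% of a liability L.
  - Shared cause: L = aV + uU + noise.
  - Follows from the outcome: L = aV - uY + noise.
- Y is regressed on V alone, then on V and C.

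Without adjustment the coefficient was -0.300 to -0.301. After adjusting for C:

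| a | u | Shared cause | Follows from the outcome |
|---|---|---|---|
| 0.2 | 0.3 | -0.294 | -0.276 |
| 0.2 | 0.6 | -0.282 | -0.250 |
| 0.4 | 0.3 | -0.290 | -0.265 |
| 0.4 | 0.6 | -0.268 | -0.231 |
| 0.6 | 0.3 | -0.287 | -0.255 |
| 0.6 | 0.6 | -0.253 | -0.216 |

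Smallest shrinkage: 1 - 0.294/0.300 = 2%. Largest: 1 - 0.216/0.300 = 28%. All twelve scenarios moved towards zero. This covers a single binary complication; deaths were not simulated separately.

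**The case against.** The strongest reply is that section 16 is a data-handling inventory and not the analysis plan. Its label is qualified by relevance, section 14.1 names no covariates, and the diagram of the hypothesised model was not visible in the text reviewed. This stands in part. A reader might infer that the model does condition on its own outcomes; the documents support only that it would, if the stated role is followed. The qualifier does not remove the conflict, however. It governs which measures are used, while the parenthesis says what they are used as.

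Second, the five named neonatal indicators lie outside the control blocks. That is correct, and it limits the point to complications, deaths, NICU time, length of stay, labour details, interventions and care processes.

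Third, vulnerability and resilience are measured again postpartum (section 12.3.2), and the depression scale is also collected at survey 2 (section 12.3.2.1). Birth events precede those measures, so adjusting for them on paths to survey 2 can be legitimate. Interventions and care processes can also be modelled as mediators. This stands, and it rules out a blanket ban on using these variables.

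Fourth, a reader might infer a much larger bias by supposing that a continuous severity marker is controlled as well. With a marker correlated λ with neonatal health, the coefficient becomes -0.3(1 - λ²)/(1 - 0.09λ²). That is -0.230 at λ = 0.5 and -0.089 at λ = 0.85, a loss of 23% to 70%. The documents do not support that range: length of hospital stay is listed under complications for the parent, and no infant marker of this kind is named.

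**Conclusion.** The point holds as a wrongly stated role. Section 16 assigns control status to events that sections 4.3, 12.3.1.1, 14.1 and 16.2 treat as outcomes or as things to be assessed, and no visible text resolves the conflict. If the label is followed, the paths from survey 1 vulnerability and resilience to birth and neonatal outcomes would be attenuated or distorted. The illustrative shrinkage of about 2% to 28% for a single complication rests wholly on assumed values: a true effect of -0.30, a complication in 10% of births, and the values of a and u above. It shows direction and a plausible range and is not a forecast. The text does not show that the fitted model will adjust in this way, and the point does not extend to paths that end in survey 2 measures.

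**What to change.** Reconcile the two labelled blocks in section 16 with sections 12.3.1.1 and 16.2 by giving each variable one role per path:

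- **Covariates:** pre-existing conditions and demographics.
- **Outcomes:** complications, NICU time, length of stay, pregnancy loss, and infant and maternal death.
- **Outcomes or explicitly modelled mediators:** length of labour, interventions and infant care processes.
- **Further tests:** a role for each, according to when the test is done relative to survey 1.

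Then state that none of the post-exposure variables is a control on paths from survey 1 constructs to birth or neonatal outcomes, and that they may enter as preceding variables on paths to survey 2 measures.

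The cost is protocol wording only; the same data are extracted. The roles should be settled before any model is fitted, because section 7 schedules analysis from the first day of data collection and an open adjustment set invites data-driven choices.
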